8.2.2. Multiple-dose Phase

Following review of data related to the efficacy, safety, tolerability, and PK from the single-dose phase, the IDMC will provide a recommendation for a dose (for each age group) to be carried forth into the double-blind, placebo-controlled multiple-dose phase to assess efficacy of oxymorphone HCl vs. placebo. The determination of dose to be tested in the multiple-dose phase will be made independently for each age group. The IDMC will make their dose recommendation after equal consideration of the following factors:

- 1) Analgesic efficacy in the single-dose phase (no morphine-NCA bolus doses required for at least 3 hours following dosing).
- 2) PK and analgesic efficacy data from the multiple-dose phase of the preceding age group.
- 3) Minimal drug-related AE profile (determined at the discretion of the IDMC).
- 4) Optimal safety and tolerability profile (determined at the discretion of the IDMC).

In the event that no dose tested in the single-dose phase meets these criteria, the IDMC will provide a dose recommendation for testing in the multiple-dose phase that they deem safe for

testing (the dose may be below the lowest dose tested in the single-dose phase, but not above the highest tested dose). For any cohort or age group, the Sponsor may choose to utilize a dose for the multiple-dose phase other than that recommended by the IDMC, but will notify the IDMC of any such changes and provide rationale for the change prior to implementing the change in the study. All such changes must be endorsed as “safe to proceed” by the IDMC before being implemented in the study.

8.3. Study Drug Administration

Study drug in the form of oral liquid will be provided for subjects in age groups A and B. If a subject in groups A or B does not consume the entire dose, the subject should not be redosed until the next time scheduled dose, if applicable. A parenteral formulation of the study drug will be provided for subjects in age groups C and D. Subjects randomized to receive placebo in the double-blind multiple-dose phase will be administered an oral liquid or parenteral formulation (depending on age group) that is identical in appearance to the active study drug.

The selection and timing of drug dosing will be as presented in Table 3 and Table 4 (Schedule of Events).

Following surgery, when subjects in Groups A and B are showing signs of tolerating oral intake and Subjects in Group C and D are showing signs of awakening and arousal their SOC postoperative analgesic regimen will be discontinued. All subjects will then be closely monitored for pain (pain scores will be recorded at least hourly) and they will be administered study drug or placebo once their pain score is ≥ 4 on the FLACC or ≥ 3 on the NIPS (day 1 time zero). Subjects in Groups A and B must be able to tolerate oral intake prior to receiving oxymorphone oral liquid. Background morphine-NCA (section 8.1.4) will be initiated coincident with study drug/placebo administration. No food or oral liquid restrictions will be imposed around the time of dosing. All subjects will receive morphine-NCA rescue as needed. The study drug will be administered every 4 to 6 hours as needed (q4-6h PRN) in the double-blind multiple-dose phase. Following dose 1, subsequent doses should be administered no less than 4 hours apart, and at least 20 minutes have elapsed since the last bolus NCA rescue. The last dose of study drug will be administered no later than 18h post first dose. All subjects must receive a minimum of 3 doses of study drug in the multiple-dose phase.

8.3.1. Age Groups A and B

Subjects in age groups A and B will receive an oral formulation of oxymorphone HCl (or an oral liquid placebo matched in color and flavor). Morphine-NCA will be administered by IV catheter.

8.3.2. Age Groups C and D

Subjects in age groups C and D will receive a parenteral formulation of oxymorphone HCl (or a matched placebo appropriate for parenteral administration) administered as a bolus dose through their existing IV catheter (already in place for morphine-NCA).

8.4. Discussion of Study Design, Including the Choice of Control Groups

This is a Phase 3, post market PREA commitment with an open-label, single-dose, dose selection phase and a randomized, double-blinded, placebo-controlled multiple-dose phase to characterize

the safety, tolerability, PK, and efficacy of oxymorphone HCl immediate-release oral liquid in pediatric subjects with acute moderate to severe postoperative pain. The study design and the use of placebo as a control are necessary to provide reliable scientific evidence of efficacy, safety, tolerability, and PK to ensure a reliable evaluation of the balance of benefits and risks.

Within each treatment cohort and age group, subjects will receive open-label oxymorphone HCl immediate-release oral liquid (Age Groups A and B) or IV (Age Groups C and D) in the single-dose phase, and either oxymorphone HCl or placebo in a 1:1 ratio in the multiple-dose phase. Enrollment will be approximately evenly distributed across each of the age groups. Sites will access an Interactive Web Response System (IWRS) for assignment of treatment phase and dose for all subjects. The age groups of subjects are:

- A. 6 months – <2 years (up to and inclusive of 729 days)
- B. 61 days – <6 months (up to and inclusive of 179 days)
- C. 31 days – 60 days
- D. 0 – 30 days

The study will initiate with oldest age subjects first (Group A), and each subsequently younger age group (B, C, and D) will enter the study only after the preceding age group has completed enrollment and the data is reviewed by an IDMC to evaluate efficacy, safety, tolerability, and PK (ie, Group A must complete enrollment and IDMC review before Group B can open for enrollment, etc.). The study will be implemented in 2 phases and will be conducted in each age group separately and sequentially:

- Beginning with Group A, each group must complete the single-dose phase and IDMC review before the next age group can open enrollment in the single-dose phase.
- Beginning with Group A, each age group must complete the multiple-dose phase and IDMC review before the next age group can open enrollment in the multiple-dose phase.

Each age group must complete their respective single-dose phase and IDMC review before proceeding to the multiple-dose phase. Up to 3 doses may be tested in each age group in the single-dose phase, and only a single dose level (determined independently for each age group) will be used to assess efficacy versus placebo in the double-blind multiple-dose phase.

8.4.1. Single-dose Phase

The treatment assignment for the single-dose phase is summarized in [Table 7](#).

Table 7: Treatment Assignment – Single-dose Phase

Age Group	Oxymorphone HCl (Max N)
6 months – <2 years ^a	15
61 days – <6 months ^b	15
31 days – 60 days	15
0 – 30 days	15

Age Group	Oxymorphone HCl (Max N)
Total	60

^a Up to and inclusive of 729 days.

^b Up to and inclusive of 179 days.

8.4.2. Multiple-dose Phase

The multiple-dose phase will proceed using the same age group stratification used in the single-dose phase. Subjects will be randomized to receive either oxymorphone HCl or placebo in a 1:1 ratio. The treatment assignment for the multiple-dose phase is summarized in Table 8.

Table 8: Treatment Assignment – Multiple-dose Phase

Age Group	Oxymorphone HCl (N)	Placebo (N)
6 months – <2 years ^a	5	5
61 days – <6 months ^b	5	5
31 days – 60 days	5	5
0 – 30 days	5	5
Total	20	20

^a Up to and inclusive of 729 days.

^b Up to and inclusive of 179 days.

9. SELECTION AND WITHDRAWAL OF SUBJECTS

9.1. Subject Inclusion Criteria

In order to be eligible to participate in the study, subjects must meet the following criteria:

1. Is male or female <2 years of age at the time of surgery.
2. Must weigh at least 3 kg.
3. Is scheduled to have a surgical procedure for which opioid analgesia will be needed to manage postoperative pain for at least 18 hours following intraoperative and/or postoperative IV analgesia.
4. Is generally healthy as documented by medical history; physical examination (including, but not limited to, the cardiovascular, gastrointestinal, respiratory, and central nervous systems); vital sign assessments; 12-lead electrocardiograms (EKG); clinical laboratory assessments; and general observations. Any abnormalities or deviations from the acceptable range that might be considered clinically relevant by the study physician or Investigator will be evaluated on a case-by-case basis, agreed upon by the principal Investigator (or sub-investigator), and documented in study files before enrolling the subject in the study.
5. The subject's parent or guardian has been informed of the nature of the study and has provided written informed consent.

Postoperative

6. Is anticipated to require an analgesic regimen using a short-acting opioid (non-oxycodone or non-oxymorphone) analgesic after surgery (according to SOC as defined in the protocol).
7. Is an inpatient expected to be hospitalized for 24 hours after dosing with study drug.
8. Has an indwelling access catheter for blood sampling.
9. For Groups A and B: Has demonstrated signs of tolerating oral intake. All infants and children should be able to demonstrate strong suck and swallow reflexes and neurologic alertness and stability sufficient to handle oral secretions.

Prior to Administration of Oxymorphone HCl Oral Solution

10. For Groups A and B: Has demonstrated the ability to tolerate clear liquids, following surgery according to the SOC at each institution. All infants and children should be able to demonstrate strong suck and swallow reflexes and neurologic alertness and stability sufficient to handle oral secretions. The ability to tolerate small amounts (1 to 2 oz.) of clear liquids without emesis (over 30 to 60 minutes) would support readiness for study participation and oral intake once the physician has ordered the diet advanced to clear liquids and the subject has ingested fluids by mouth without nausea or vomiting.

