
Name of Sponsor/Company: Endo Pharmaceuticals Inc.					
Name of Investigational Product: EN3319 Oxymorphone HCl Immediate-release Oral Liquid and Oxymorphone HCl injection					
15. Subject (and/or mother if subject is nursing) has participated in a clinical study of an unapproved drug within the previous 30 days.					
16. Is not suitable for entry into the study in the opinion of the Investigator.					
Investigational Product, Dosage, and Mode of Administration: EN3319 oxymorphone HCl immediate-release oral liquid (Groups A and B) 1 mg/mL dosed at 0.05 mg/kg by mouth, with subsequent doses to be determined by IDMC. Oxymorphone HCl IV solution (Groups C and D) 1 mg/mL at doses to be determined by IDMC.					
Duration of Study:					
Screening period – up to 5 days					
Treatment period – up to 24 hours					
Follow-up telephone contact – 3±1 and 14 ±2 days after the last dose of study drug					
Reference Therapy, Dosage, and Mode of Administration: Morphine NCA					
	Starting Background (mcg/kg/h)	Maximum Background (mcg/kg/h)	Bolus Dose (mcg/kg)	Lockout (minutes)	Maximum Bolus/h
Age Group					
A and B	Up to 5	Up to 30	10-15	10	3
C and D	0	Up to 15	10	10	3
Criteria for Evaluation:					
Efficacy: Analgesic efficacy will be characterized for subjects in all age groups by assessing morphine demand using NCA. The incidence, amount of NCA rescue medication (both basal infusion and bolus morphine doses), and time to first bolus rescue used in each group will also be examined. Pain assessments using age-appropriate instruments (NIPS and FLACC) will also be utilized.					
Pharmacokinetics:					
Non-compartmental PK parameters such as AUC, T _{max} , and C _{max} will be determined after a single dose of oxymorphone. Oxymorphone plasma concentration-time data after multiple dosing will be evaluated using population PK analysis methods. Full details of the population PK modeling and analysis will be documented in a separate population PK analysis plan.					
All data available for oxymorphone dosing and sample concentrations with elapsed time from the last dose will be reviewed for use in the analysis. A structural and error model will be selected based on oxymorphone plasma concentration time profiles.					
Once the structural model has been selected, covariates will be added to the model. Covariates that will be studied include age and weight and others as appropriate.					
Safety and Tolerability:					

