Table 4) will be collected following randomization. The FLACC will be used for subjects in Groups A and B. The NIPS will be used for subjects in Groups C and D. All subjects will then be closely monitored for pain and their pain score will be recorded at least hourly until their pain score is ≥ 4 on the FLACC or ≥ 3 on the NIPS, at which time they will be administered study drug (oxymorphone HCl immediate release oral liquid for Groups A and B; IV oxymorphone HCl for Groups C and D) or placebo. Subjects in Groups A and B must be able to tolerate oral intake prior to receiving oxymorphone oral liquid. Morphine-NCA (section 8.1.4) will be initiated coincident with but not earlier than study drug/placebo administration, and this time will be designated as day 1 time zero. No food or oral liquid restrictions will be imposed around the time of dosing. All subjects will receive morphine-NCA rescue as needed. Subjects will undergo subsequent pain assessments at half-hour intervals post first dose in the multiple-dose phase (Table 4). Following dose 1, subsequent doses should be administered q4-6h PRN but no less than 4 hours apart, and at least 20 minutes have elapsed since the last bolus NCA rescue. The last dose of study drug will be administered no later than 18h post first dose. (All subjects must receive a minimum of 3 doses of study drug in the multiple-dose phase). PK and additional assessments will occur at fixed intervals throughout the multiple-dose phase, as outlined in section 3. Food consumption will be recorded from the period 1 hour prior to administration of study drug through EOT assessment; record all times that any food was consumed and what food was consumed (DAT, DAT-soft, FF, CF, water, formula, breast milk).

Following first administration of study drug, procedures and assessments will include the following:

- Blood samples for PK analysis should be collected immediately prior to each dose. Post-dose vital signs, respiratory assessments, and neurological assessments will be recorded at 0.5, 1, 2, 3, and 4 hours after administration of first dose of study drug; and at 0.5, 1, and 2 hours after administration of subsequent doses.
- Continuous telemetry.
- Continuous pulse oximetry.
- AEs and concomitant medications will be monitored throughout the multiple-dose phase.
- Pain assessments (using FLACC or NIPS; see Appendix C or Appendix D, respectively) will be recorded every 0.5 hours through EOT.

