8.1.7. End-of-treatment/Early Termination

At the completion of the single- or multiple-dose phases, EOT assessments and procedures will occur at 24 hours after the last study drug administration or upon early study withdrawal. Each subject will be required to complete all EOT/ET assessments and procedures unless consent has been withdrawn. EOT assessments will include:

- Ongoing collection of AEs/SAEs (section 12).

- Performing physical examination: a brief physical examination, excluding length and weight, to assess the subject's overall health and physical status.
- Measuring vital sign (section 12.8).
- For the single-dose phase, collecting a blood sample for PK assessments (at 24 hours or upon EOT, if possible).
- For multi-dose phase, no blood sample for PK assessments will be drawn at EOT.
- Obtaining clinical laboratory tests (section 12.7): clinical laboratory tests as part of SOC will be acceptable.
- Assessing respiratory and neurological function (section 12.10, section 12.11 and Appendix A).
- Telemetry and pulse oximetry will be ongoing to EOT or ET.
- Updating and recording concomitant medications (including NCA rescue medications).
- Pain assessment (FLACC or NIPS; Appendix C or Appendix D, respectively) will be recorded.
- Recording of food consumption from the period 1 hour prior to administration of study drug through EOT assessment; record all times that any food was consumed and what food was consumed (DAT, DAT-soft, FF, CF, water, formula, breast milk).
- Converting subjects to a marketed opioid upon discharge, if required.
- Scheduling the 3-day and 14-day follow-up telephone call: assessment to include ongoing or new AEs, SAEs, and associated concomitant medications. The complete Schedule of Events is provided in Table 3 and Table 4

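### Inclusion 7 asks for a 24 h stay without naming the dose, while multiple-dose assessments run to 24 h after the last dose, 32 to 42 h after the first

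*Protocol*

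**What the plan says.** Criterion 7 (Protocol 9.1, repeated in the Synopsis) is a single sentence covering both phases: "Is an inpatient expected to be hospitalized for 24 hours after dosing with study drug". It names neither first nor last dose.

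For the multiple-dose phase:

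- **Dosing (Protocol 8.1.6).** "subsequent doses should be administered q4-6h PRN but no less than 4 hours apart"; "All subjects must receive a minimum of 3 doses of study drug in the multiple-dose phase"; "The last dose of study drug will be administered no later than 18h post first dose".
- **EOT (Protocol 8.1.7).** "EOT assessments and procedures will occur at 24 hours after the last study drug administration or upon early study withdrawal".
- **Procedures that run to EOT.** Pain scores "will be recorded every 0.5 hours through EOT" (8.1.6); "Telemetry and pulse oximetry will be ongoing to EOT or ET" (8.1.7). Examination, vital signs and laboratory tests are due at EOT itself. NCA morphine is recorded continuously after the first dose.
- **Other 24 h frames.** Protocol 10.2 restricts other analgesics during a 24-hour assessment period with no stated start. The same section describes recording concomitant medication while on study drug up to 24 h after the first dose. SAP 3.6 and 6.3.1.2 also count 24 h from the first dose, but SAP 4.4 counts it from the last.
- **Primary variable.** Protocol 11.1.1 defines it as total morphine, background plus boluses. Protocol 14.5 compares it over the multiple-dose phase and gives no hour limit.

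**The concern.** The pain scores, telemetry, oximetry and IV morphine recording all need the infant in hospital. If criterion 7 is applied as 24 h from the first dose, an infant can satisfy it and leave before these are complete. The late pain scores and monitoring would then be missing, and the final laboratory tests and vital signs would be taken early. Protocol 9.3.1.2 does not allow replacement in this phase.

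The morphine total raises a related problem even if every infant stays to EOT. Study drug is given as needed, so the time of the last dose, and with it EOT, is fixed only after randomisation. A total taken to EOT mixes how much morphine an infant needed with how long it was counted.

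**Working it through.** **The plan's own figure.** Protocol 8.1 gives a multiple-dose duration of up to 17 days from first dose to last follow-up. The last contact is 14 ± 2 days after the last dose.

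18 h ÷ 24 + 14 + 2 = 0.75 + 16 = 16.75 days

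This rounds to the stated 17 days, so the 18 h limit and last-dose counting are the timings the plan itself uses.

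**Inputs for EOT**

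| Input | Value | Source |
|---|---|---|
| Latest last dose | 18 h after first | Protocol 8.1.6 |
| Minimum doses | 3 | Protocol 8.1.6 |
| Minimum interval | 4 h | Protocol 8.1.6 |
| EOT | 24 h after last dose | Protocol 8.1.7 |
| Required stay | 24 h, dose not named | Protocol 9.1 |
| Pain scores | every 0.5 h to EOT | Protocol 8.1.6 |

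**EOT measured from the first dose**

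- Earliest for a completer: (3 − 1) × 4 + 24 = 32 h.
- Latest: 18 + 24 = 42 h.

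**If the required stay runs from the first dose**, gap = EOT − 24 h; scheduled scores = EOT ÷ 0.5; scores after hour 24 = gap ÷ 0.5.

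| | Earliest EOT | Latest EOT |
|---|---|---|
| EOT | 32 h | 42 h |
| Gap | 8 h | 18 h |
| Scores scheduled | 64 | 84 |
| Scores after hour 24 | 16 | 36 |
| Share | 16/64 = 25% | 36/84 = 43% |

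**If it runs from the last dose**, the required stay ends at EOT and the gap is 0 h.

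**Single-dose phase.** There is one dose, so both readings end at 24 h and there is no gap.

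**Unequal morphine windows.** Assume totals run to EOT, since no other limit is given. Completers are then counted for 32 to 42 h. Assuming a constant hourly demand, purely for illustration, 42 ÷ 32 = 1.31. Two infants with the same hourly need could differ by up to 31% in total.

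**The case against.** The strongest reply is that the first dose is read into criterion 7. Elsewhere the protocol says first dose when it means it. Twenty-four hours after dosing ends would match EOT in both phases. Protocol 8.1.7 also places conversion to a marketed opioid at discharge among the EOT procedures, which suggests discharge at or after EOT. It asks every subject to complete EOT or early-termination assessments unless consent is withdrawn, so an infant who leaves early should still have final assessments. And the criterion is an expectation at entry, not a discharge rule.

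Most of this stands, and it is why the gap is conditional. It does not settle the reading. The criterion is applied before the first dose, when the time of an as-needed last dose is unknown. No passage requires the stay to last until EOT, and the 24 h recording window in Protocol 10.2 does run from the first dose. Early-termination assessments supply a final set of values, but not the pain scores and monitoring that would have followed.

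Three stronger readings are tempting, and the documents do not support them:

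- **That up to 18 h of data will be lost.** This is the upper end of one reading.
- **That the Synopsis line "Treatment period – up to 24 hours" is out of date.** A last dose by 18 h plus one interval of 6 h gives 24 h, so the line fits the current schedule if treatment period and EOT are separate things.
- **That truncation will differ by arm because sicker infants stay longer.** Randomisation is 1:1 within age group and blinded, so baseline sickness is not tied to arm. The time of the last as-needed dose could depend on treatment because it comes after randomisation, but nothing in the documents shows that it does.

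It is also fair to say that the SAP removes all efficacy and PK analyses after early termination (SAP 3.4, 3.15 and 8). That reduces the present consequence considerably.

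**Conclusion.** The point holds as an unresolved anchor with a conditional gap. For completers of the multiple-dose phase, scheduled in-hospital observation ends 32 to 42 h after the first dose. It exceeds the stay required for eligibility by 8 to 18 h if that stay is counted from the first dose, and by nothing if it is counted from the last. The range assumes at least three doses at the permitted spacing and the 18 h limit on the last dose.

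The unequal morphine window does not depend on how criterion 7 is read. It follows from as-needed dosing, EOT tied to the last dose, and the absence of an hour limit on the total.

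What remains at stake is descriptive: the multiple-dose summaries of total morphine and its duration (SAP 7.7), EOT/ET laboratory results (7.8.3), vital signs and oxygen saturation (7.8.5), and sedation and apnoea (7.9.1). These still matter, since SAP 1 gives the risk of respiratory depression as the reason for the IDMC's recommendation. The point is worth correcting, but it does not undermine the design.

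**What to change.** 1. **One named anchor.** Reconcile criterion 7 (Protocol 9.1 and Synopsis), the 24-hour assessment period and concomitant-medication window in Protocol 10.2, and the windows in SAP 3.6, 4.4 and 6.3.1.2 with the EOT definition in Protocol 8.1.7. Each should say first or last dose. Which anchor to use, and so how long a stay to require, is for the sponsor. The analgesic restrictions in Protocol 10.2 and 10.2.1, and the allowance after EOT in 10.1.5, should be checked against the chosen anchor so that they cover the same hours.
2. **One morphine window.** Total cumulative morphine over a common fixed period from first dose that lies inside the required stay. A window of no more than 24 h meets this on either reading of criterion 7. Apply it in the primary definition (Protocol 11.1.1 and 14.5) and in the SAP 7.7 summary, and report hours observed per subject so that any truncation is visible.

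**Cost.** The changes are to wording and one derivation. Eligibility may narrow slightly if the required stay becomes longer. Morphine given after the fixed window would drop out of the main total but can be reported separately. With the study stopped, the SAP changes are the part that can still affect the report.
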